23.2.1.4 Assigning Week to eDiary Assessments

The day of an infusion starts a new week e.g. the day of the first infusion is the first day of Week 1.

Weekly assessments coming from the eDiary will be assigned to a week using the day of an infusion as a starting point. Thus, the windowing showed in [Panel 6](#) will be applied.

Panel 6 Windowing of Weeks – Weekly eDiary Assessments

Days since IMP	First IMP	Second IMP	Third IMP	Fourth IMP
28 to 37	Week 5	Week 17	Week 29	Week 41
38 to 44	Week 6	Week 18	Week 30	Week 42

Days since IMP	First IMP	Second IMP	Third IMP	Fourth IMP
45 to 51	Week 7	Week 19	Week 31	Week 43
52 to 58	Week 8	Week 20	Week 32	Week 44
59 to 65	Week 9	Week 21	Week 33	Week 45
66 to 72	Week 10	Week 22	Week 34	Week 46
73 to 79	Week 11	Week 23	Week 35	Week 47
80 until the next IMP	Week 12	Week 24	Week 36	Week 48

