The content of the cluster headache diary is developed on key characteristics as mentioned in the definition of cCH (see section 9.1.2). The eDiary consists of applications and reports which will be used to derive the cluster headache endpoints and abortive medication use. The patient should record for each day/week if they experienced any cluster headache attacks. For each experienced cluster headache attack, the start date and time will be collected. The patient will record further daily/weekly information regarding the severity of pain associated to cluster headache and intake of cluster headache abortive medication. Cluster headache items will be assessed with a yes/no response; and severity of pain will be rated on an ordinal scale ranging from 0 to 4 (headache pain ratings: 0=none/barely any pain; 1=mild; 2=moderate; 3=severe; 4=excruciating).⁴⁸ Additional details regarding the questions that patients will answer can be found in the *eDiary Training Module*.

The Screening Visit will correspond to the day of eDiary distribution and will start the 28-day eDiary Screening Period. Any patient found to be ineligible for the study during Screening Period will not be enrolled. An *eDiary Eligibility Report* will be used to review baseline cluster headache attack days and eDiary compliance during the Screening Period for the eligibility assessment of:

- a minimum 14 cluster headache attacks for the first 28 days of Screening Period
- compliance by entry of cluster headache data for at least 24 out of the first 28 days of Screening Period.

On the Baseline Visit (Day 0/Visit 2), patients must ensure to complete eDiary recording of cluster headache attacks that ended prior to infusion (that is for cluster headache attacks which are ongoing or not yet recorded in the eDiary).

On each day during the first 4 weeks that follow each eptinezumab infusion, the patient will be asked to record eDiary data for the day. On Weeks 5 to 12, 17 to 24, 29 to 36, and 41 to 48, and until the Completion Visit (Week 48/Visit 14)/Withdrawal Visit, the patient will be asked to record eDiary data for the week.

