3.1 Definition of Baseline

For the efficacy endpoints based on the eDiary, e.g. the number of cluster headache attacks, the data collected during the first 28 days of the Screening Period will be used to calculate the baseline value for the endpoints. In case of a 7-day extension of the Screening Period, the last 21 days of the original 28 days Screening Period and the first 7 days of the extension will be used to calculate the baseline value (if the extension is less than 7 days the days used prior to the extension should be changed accordingly ending up with a total of 28 days). Furthermore, in case of re-screening, the baseline values will be calculated based on the first 28 days of the re-screening period. See section [13.5.1.1.1](#) and chapter [23](#) for handling of missing data.

For the endpoints not based on the eDiary, the baseline value is the value captured either during the Screening Visit or at the Baseline Visit prior to the infusion, whichever is later.

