3.2 Definition of Periods

The trial consists of the following periods:

- Screening period (4 weeks): Starts at the Screening Visit and continues up to start of IMP infusion at the Baseline Visit

- Treatment period (48 weeks): Starts at the IMP infusion at the Baseline Visit and continues up to and including the Completion Visit
- Safety Follow-up period (8 weeks): Starts after the Completion Visit and continues up to and including the SFU Visit

Unless otherwise specified, the Treatment Period, and the Safety Follow-up Period will be reported as one period.

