
• To evaluate the efficacy of eptinezumab on health-related quality of life, health care resource utilization, and work productivity	
- Patient Global Impression of Change (PGIC) score at Weeks 4, 8, ..., 48- Change from Baseline in the Sleep Impact Scale (SIS) domain scores at Weeks 4, 12, 16, 24, 28, 36, 40, 48 - Exploratory endpoints:- Change from Baseline in the number of monthly attacks (Months 1, 2, ..., 12)- Change from Baseline in the pain per attack, as assessed using the 5-point self-rating pain severity scale (Months 1, 2, ..., 12)- Response: $\geq 30\%$ reduction from Baseline in the number of monthly attacks (Months 1, 2, ..., 12)- Response: $\geq 50\%$ reduction from Baseline in the number of monthly attacks (Months 1, 2, ..., 12)- Response: $\geq 75\%$ reduction from Baseline in the number of monthly attacks (Months 1, 2, ..., 12)- Response: 100% reduction from Baseline in the number of monthly attacks (Months 1, 2, ..., 12)- Change from Baseline in the monthly number of times an abortive therapy (oxygen and/or triptans, only oxygen, and only triptans) was used (Months 1, 2, ..., 12)- Change from Baseline in the weekly integrated measure of frequency and intensity of attack related pain, that is, the sum of the intensity (worst pain on a 5-point self-rating pain severity scale) for each attack during a week (Weeks 1, 2, 3, 4, 13, 14, 15, 16, 25, 26, 27, 28, 37, 38, 39, 40) or the intensity of attack related pain multiplied by the weekly number of attacks (Weeks 5, 6, ..., 12, 17, 18, ..., 24, 29, 30, ..., 36, 41, 42, ..., 48)- Use of triptans (Weeks 1-48)- Use of oxygen (Weeks 1-48)- Use of preventive medication (Weeks 1-48)- Sustained response: $\geq 75\%$ reduction from Baseline in the number of monthly attacks for any month, where all the subsequent months also had $\geq 75\%$ reduction from Baseline in the number of monthly attacks (Months 1, 2, ..., 12)- A maximum score of mild on the 5-point self-rating pain severity scale (Weeks 1, 2, ..., 48) - Secondary endpoints:- Change from Baseline in the EuroQol 5-Dimension 5-Level (EQ-5D-5L) score at Weeks 4, 16, 28, 40, and 48- Health Care Resources Utilization (HCRU) at Baseline and Weeks 4, 16, 28, 40, and 48- Change from Baseline in the Work Productivity Activity Impairment: General Health second version (WPAI:GH2.0) subscores (Absenteeism, Presenteeism, Work productivity loss, Activity impairment) at Weeks 4, 16, 28, 40, and 48

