23.2.1.2 Calculation of Baseline eDiary Assessments

Calculation of the eDiary baseline begins on the day of the Screening Visit.

In case of a 7-day extension of the Screening Period the last 21 days of the original 28 days Screening Period and the first 7 days of the extension will be used to calculate the baseline value. In case the extension is less than 7 days more days will be used from the Screening Period ending up with a total of 28 days.

When finding the baseline value for number of monthly attacks, the number of reported attacks will be scaled up to 28 days using (assuming that days with missing data are similar to the days with data):

$$28 * (\text{Reported number of attacks} / \text{Reported eDiary Days})$$

The average weekly number of attacks at baseline will be found by dividing the number of monthly attacks at baseline by 4:

$$28 * (\text{Reported number of attacks} / \text{Reported eDiary Days}) / 4$$

When finding the baseline number of times abortive medication was used the above formulas are used with *Reported number of attacks* replaced by *Reported number of times an abortive medication was taken*.

When finding the baseline values using the 5-point self-rated pain severity scale scores, three different formulas will be used. The **baseline monthly pain per attack** is found by:

Sum of reported pain across attacks/Number of reported attacks

The **baseline weekly pain per attack** equals the baseline monthly pain per attack.

The **baseline average attack related daily pain** is found by:

Sum of the average daily pain across days with data/Number of days with data

where days with 0 attacks will add a value of 0 to the nominator and count as a day in the denominator.

The **baseline monthly integrated measure of frequency and intensity of attack related pain** is found by:

$((\text{Sum of reported pain across days with data/Number of days with data}) * 28) / 4$

where days with 0 attacks will add a value of 0 to the nominator and count as a day in the denominator.

The **baseline weekly integrated measure of frequency and intensity of attack related pain** equals the baseline monthly integrated measure of pain.

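### Attacks before the first infusion on Day 0 are scored as Week 1 and Month 1 attacks. This can deny a 100% response or a remission run starting in Week 1; the effect on means is small.

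*SAP*

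**What the plan says.** **Week assignment.** SAP 23.2.1.4 states: "The day of an infusion starts a new week e.g. the day of the first infusion is the first day of Week 1". Panel 6 in the same section starts Week 5 at 28 days since the infusion, so Weeks 1-4 are Days 0-27 and Week 1 is Days 0-6. No diary rule splits the infusion day at the infusion time.

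**Baseline.** SAP 3.1: "the data collected during the first 28 days of the Screening Period will be used to calculate the baseline value for the endpoints". SAP 23.2.1.2: "Calculation of the eDiary baseline begins on the day of the Screening Visit". Protocol 8.3 puts the Baseline Visit four weeks after the Screening Visit, so baseline ends the day before Day 0. With an extended Screening Period, Protocol 8.2.4 uses the last 28 days before baseline for eligibility and SAP 3.1 again takes 28 screening days.

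**What the diary holds.** Protocol 9.2.1.2 (eDiary) says of attacks: "For each experienced cluster headache attack, the start date and time will be collected". For the Baseline Visit it adds that "patients must ensure to complete eDiary recording of cluster headache attacks that ended prior to infusion". Pre-dose Day 0 attacks are therefore in the data with a clock time.

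**Periods and question.** SAP 3.2 defines the Treatment Period thus: "Starts at the IMP infusion at the Baseline Visit and continues up to and including the Completion Visit". The Screening Period runs up to the start of that infusion. The short-term clinical question in SAP 13.5.1 concerns change in the first four weeks after infusion.

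**Outcomes that depend on Week 1.**
- SAP chapter 5 (Panel 2) lists monthly 100% response as exploratory, weekly ≥30/50/75% response as secondary, and remission as at least 4 consecutive attack-free weeks within Weeks 1-12 (and later 12-week blocks) or Weeks 1-48.
- SAP 13.5.6.2 also tabulates 100% response by week.

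**The concern.** The week rule and the period definition disagree about the hours of Day 0 before the infusion. SAP 3.2 treats them as screening; SAP 23.2.1.4 treats them as the first hours of Week 1. Since baseline has already closed, an attack in those hours enters the analysis only as a post-treatment attack, although no drug had been given.

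For a mean this hardly matters. For an outcome that requires zero attacks, one event decides the result. A patient who wakes with an attack on the morning of the first infusion and has none for the next four weeks is reported as a Month 1 non-responder at the 100% level.

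The SAP does separate pre- and post-infusion time on the infusion day elsewhere: treatment-emergent adverse events (14.1.3, 14.1.5), laboratory, ECG and vital-sign windows (23.3.2), and CGRP samples (chapter 16). The diary rule is the exception, and no reason is given.

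**Working it through.** The plan states no figure for this point, so there is none to reproduce.

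**Inputs from the documents**
- Weekly score = 7 × attacks / diary days, set to missing with 3 or fewer diary days; monthly score = 4 × sum of weekly scores / weeks observed (SAP 23.2.1.3).
- Weeks 1-2 and Weeks 1-4 contrasts are plain averages over 2 and 4 weeks (SAP 13.5.2, 13.5.1.2).
- Entry minimum: 14 attacks in 28 days (Protocol 5.3) = 3.5/week = 0.5/day.

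**Assumptions (not in the documents)**
- Attacks are Poisson and evenly spread over the day.
- Infusion is at 11:00, with a range of 08:00 to 14:00. Write f for the fraction of Day 0 before the infusion; at 11:00, f = 11/24 = 0.458.

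**1. One pre-dose Day 0 attack, none afterwards, complete diary**

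Week 1 = 7 × 1/7 = 1. Month 1 = 4 × (1+0+0+0)/4 = 1.

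| Baseline per week | Week 1 reduction | Month 1 reduction |
|---|---|---|
| 3.5 | 1 − 1/3.5 = 71.4% | 1 − 1/14 = 92.9% |
| 7 | 1 − 1/7 = 85.7% | 1 − 1/28 = 96.4% |
| 14 | 1 − 1/14 = 92.9% | 1 − 1/56 = 98.2% |

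None reaches 100%. Week 1 ≥75% response is missed when 1 − 1/b < 0.75, that is, when the weekly baseline b is below 4. With a complete screening diary, that means 14 or 15 attacks in 28 days (3.5 or 3.75/week).

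At 3.5/week this patient's change is (−2.5 − 3.5)/2 = −3.00 for Weeks 1-2 and (−2.5 − 3 × 3.5)/4 = −3.25 for Weeks 1-4. Without the pre-dose attack both are −3.50.

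If Week 1 has 3 or fewer diary days it is missing, and Month 1 can still score 0.

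**2. Remission (SAP 23.2.1.9)**

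A run must start with a zero-attack week and all its observed weeks must be zero.
- Attack-free after the infusion in Weeks 1-4 only, with a pre-dose attack: no qualifying run, so remission is lost.
- Same pre-dose attack, attack-free in Weeks 2-5: Weeks 2-5 qualify, so remission is kept.

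**3. Share of patients with at least one pre-dose Day 0 attack**

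P = 1 − exp(−rate × h/24), where h is the infusion hour.

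| Rate per day | 08:00 | 11:00 | 14:00 |
|---|---|---|---|
| 0.5 | 15% | 20% | 25% |
| 1 | 28% | 37% | 44% |

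This is not the share misclassified. For Month 1 100% response, misclassification also needs no attack in the rest of the 28 days, and the documents give no such rate. As an illustration only: if 5-10% were truly attack-free, independently of the pre-dose attack, the loss at 11:00 is 0.05 × 20% to 0.10 × 20% = 1 to 2 percentage points at 0.5/day, and 0.05 × 37% to 0.10 × 37% = about 2 to 4 points at 1/day.

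**4. Dilution of the mean**

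Let L be the daily baseline rate and r a constant proportional reduction from the infusion on. Expected Week 1 attacks under the present rule are fL + (7 − f)L(1 − r), which is fLr more than 7L(1 − r). Relative to the true change the dilution is f/14 for Weeks 1-2 and f/28 for Weeks 1-4, whatever L and r are.
- f = 0.458: 0.458/14 = 3.3% and 0.458/28 = 1.6%.
- f = 1 (upper bound): 7.1% and 3.6%.

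**5. Two ways of removing the pre-dose attacks**
- *Drop them but keep Day 0 as a full diary day.* Expected Week 1 score = (7 − f)L(1 − r), too low by fL(1 − r). This is a larger error than the present fLr whenever r < 50%. With no effect at all (r = 0) it produces a false Week 1 improvement of f/7 = 0.458/7 = 6.5%, where the present rule is unbiased.
- *Drop them and count Day 0 as 1 − f days.* With a full diary, expected score = 7 × (7 − f)L(1 − r)/(7 − f) = 7L(1 − r). This is unbiased for any r.

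**The case against.** The strongest reply is that the rule is simple, its effect on the means is trivial and conservative, and nothing turns on it: the primary endpoints are safety, there are no key secondary endpoints, and no formal testing is done. All of that stands, and it limits the weight of the point. It does not answer the zero-attack outcomes. In a single-arm descriptive study the reported percentages are themselves the result, and a responder misclassified for a pre-treatment event is an error in either direction.

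Four stronger readings are tempting but unsupported:
- **That Weeks 1-4 remission is lost as an endpoint.** No such endpoint exists. Remission is any qualifying run within a longer window, so only a run confined to Weeks 1-4 is lost.
- **That 15-44% of patients are misclassified.** That is the share with any pre-dose attack. Month 1 100% response also stays possible when Week 1 is missing.
- **That the same error occurs at infusions 2-4.** Those hours are already post-baseline, so at most attacks move between adjacent weeks. The diary is in weekly mode beforehand, must be completed before the infusion (Protocol 8.4), and Panel 6 runs the last window until the next infusion. Attacks that morning may already be in the Week 12, 24 or 36 entry. The instruction on attacks that ended before infusion is given for the Baseline Visit only.
- **That Weeks 1-2 was chosen to show fast onset.** SAP 13.5.2 gives no reason, and Protocol 3.2 names Weeks 1-2 as the primary endpoint window of the episodic cluster headache study.

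**Conclusion.** The point holds for Day 0. SAP 23.2.1.4 scores attacks from before the first infusion as Week 1 and Month 1 attacks, against SAP 3.2 and against a clinical question about the time after infusion. With at least 4 diary days in Week 1, one such attack is enough to exclude Month 1 100% response, the weekly 100% response tabulated for Week 1, and any remission run beginning in Week 1. On its own it defeats Week 1 ≥75% response only just above the entry minimum.

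How many patients this touches depends on infusion time and attack pattern, neither of which is documented, and on how many patients have no later attack. The bias in the mean changes is not a reason to act by itself. The case for change is the accuracy of the zero-attack outcomes and the consistency of the SAP. It is worth correcting but does not affect the study's primary conclusions.

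**What to change.** In SAP 23.2.1.4, state that on Day 0 an attack, with its pain rating and abortive use, counts in Week 1 only if its recorded start is at or after the start of the infusion. Count Day 0 in the prorating denominator of SAP 23.2.1.3 as the fraction of the day after infusion start. Do not keep it as a full day, for the reason in step 5.

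A simpler alternative is to leave the weekly counts and the MMRM on calendar days and apply the start-time rule only to 100% response, remission and conversion. This avoids part-day prorating, which SAP 23.2.1.3 does not currently provide for.

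For infusions 2-4, do not move attacks to the preceding week unless it is confirmed that the weekly entry completed before the infusion does not already include them. Otherwise they could be counted twice.

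The cost is a short SAP addition and one derivation. Attack start times are collected in the diary and infusion start times are listed under SAP chapter 11, so no new data are needed. The downside is that, where the rule is applied, Week 1 is a fraction of a day short.

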23.2.1.5 Calculation of Assessments for Intercurrent Events

Withdrawal from Treatment

When considering withdrawal from treatment data that are collected 3 months or more after the latest infusion will be excluded. Thus, for the daily entries, data occurring 84 days or more after the date for withdrawal from treatment will be removed. For the weekly entries, if at least one day of the 7-day period is covered by 84 days or more then data will be removed.

Use of Transitional Treatment

When considering the use of transitional treatment, data are excluded 7 days after the use of transitional treatment. Thus, for the daily entries, data that occur on 1 to 7 days after the date of use of transitional treatment will be removed. For the weekly entries, if the 7-day period is including at least 1 of the days in the 7-day period after use of transitional treatment data will be removed.

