1.3 Exploratory Objective

To explore the target engagement of eptinezumab to CGRP.

2 Trial Design

This is an interventional, open-label, fixed-dose multiple administration trial to evaluate the long-term treatment with eptinezumab in participants with cCH.

An overview of the trial is presented in [Panel 1](#) and the scheduled trial procedures and assessments are summarized in [Appendix IV](#).

The target population for this trial is defined as participants with cCH, based on the *International Headache Society* International Classification of Headache Disorders third edition (IHS ICHD-3) classification, with documented evidence of cCH prior to screening and confirmed via prospectively-collected information in the eDiary during the Screening Period. A minimum of 14 cluster headache attacks must be captured in the eDiary for the 28-day Screening Period.

The total trial duration from the Screening Visit to the Safety Follow-up (SFU) Visit is approximately 60 weeks and includes Screening Period (4 weeks), Treatment Period (48 weeks), and SFU Period (8 weeks).

Eligible participants will receive four infusions with eptinezumab 400 mg at 12-week intervals at Day 0 (Visit 2), at the end of Weeks 12 (Visit 5), 24 (Visit 8) and 36 (Visit 11), administered as an intravenous (IV) infusion of 45 minutes (+15 minutes).

The SFU Visit will take place at Week 56 (Visit 15); that is, 20 weeks (5 half-lives) after the last eptinezumab administration.

Participants who withdraw from study, except for those who withdraw their consent, will be asked to attend a Withdrawal Visit as soon as possible and a further SFU Visit, scheduled 20 weeks (5 half-lives) after the last eptinezumab administration.

Participants who are withdrawn from the treatment will be given the opportunity to remain in the trial at the discretion of the investigator. Participants will be expected to attend all scheduled trial visits and procedures except eptinezumab administration. If participants refuse, they will be asked to attend a Withdrawal Visit as soon as possible and a further SFU Visit, scheduled 20 weeks (5 half-lives) after the last eptinezumab administration.

Eligibility will be assessed during the Screening Period and before the first administration of eptinezumab at the Baseline Visit (Day 0/Visit 2).

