3.4 Definition of a Month

A Month is referring to a 28-day period.

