
Objectives	Endpoints
Exploratory Objective 
To explore the target engagement of eptinezumab to calcitonin gene-related peptide (CGRP)	
Exploratory endpointChange from Baseline in CGRP (CGRP-eptinezumab complex, free CGRP) at Weeks 12, 24, 36, and 48

6 Analysis Sets

The following analysis sets will be used to analyse and present the data:

- all-participants-enrolled set* (APES) – all enrolled participants
- all-participants-treated set* (APTS) - all participants in the APES who received infusion with eptinezumab
- full-analysis set* (FAS) - all participants in the APTS who have a valid assessment of the baseline number of weekly attacks and a post-baseline assessment of number of weekly attacks.

The participants and data will be classified into the analysis sets during a *Classification Meeting* according to the definitions above after the trial database has been released, but prior to the headline results meeting.

Safety analyses (including tolerability and exposure), disposition, demographics and baseline characteristics will be based on APTS.

Efficacy analyses will be based on FAS.

Three Data Point Sets (DPS) will be used for presenting the results using eDiary data:

- DPS1: All data points obtained at or after enrolment
- DPS2: All data points obtained at or after enrolment except for those following the 7-day rule after the use of transitional treatment (for details see section 23.2.4)
- DPS3: All data points obtained at or after enrolment except for those following the 7-day rule after the use of transitional treatment (see section 23.2.4) and those following the 12-week rule after withdrawal from treatment (see section 23.2.1.5)

DPS1 will be used for the descriptive statistics described in chapter 7 as well as the sensitivity analyses described in sections 13.5.9.1 and 13.5.9.2, DPS2 will be used for the short-term efficacy estimand described in section 13.5.1, and DPS3 will be used for the long-term efficacy estimand (section 13.5.3), the sensitivity analysis described in section 13.5.9.3, and analyses based on eDiary data. For more details see chapter 13.

For efficacy data not derived from the eDiary all analyses will be based on all data points obtained at or after enrolment.

7 Descriptive Statistics

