13.5.3 Long-term Efficacy Estimand

The long-term efficacy estimand is the mean change from Baseline in the monthly number of attacks (Months 1-12) for participants with chronic cluster headache receiving IV infusion of eptinezumab 400 mg every 12 weeks, without the use of transitional treatment (GON block and oral steroids), and with continuation of treatment eptinezumab 400 mg for 12 months, and regardless of use of abortive and preventive medication for cluster headache, and infusion interruption or termination before full dose is received.

The approach described in section 13.5.1 also apply for the long-term estimand with a few adjustments:

- The **clinical question of interest** is changes in cluster headache attacks within the 12 months after infusion with eptinezumab 400 mg.
- The **endpoint to be obtained to address the clinical question** is change from Baseline in the monthly number of attacks (Months 1-12)
- The **population level summary** will be the mean change across Months 1-12
- The **intercurrent events** use of transitional treatment and interruption or termination of IMP such that full dose is not received will be handled as in section 13.5.1. Furthermore, when the primary reason is either “Lack of Efficacy” or “Adverse Events” for withdrawal from treatment this will be considered an intercurrent event that will be handled by a hypothetical strategy

Intercurrent Events

In addition to the intercurrent events described above, the following intercurrent event, occurring after treatment initiation and potentially affecting either the interpretation or the existence of the measurements associated with the clinical question of interest, is considered.

- Withdrawal from treatment due to “Lack of Efficacy” or “Adverse events” –
Hypothetical strategy

For participants withdrawing from treatment, the majority of the effect is expected to be seen within the first 12 weeks following their last infusion and therefore data that occur beyond 12 weeks after their last infusion will not be considered.

Estimator

The intercurrent event withdrawal from treatment will be handled by a hypothetical strategy estimating the effect where all participants continue their treatment with eptinezumab 400 mg for 12 months by not including data collected 3 months or more after the latest infusion.

Furthermore, the following adjustments are needed compared to the estimator in section 13.5.1

- The week variable in the MMRM will be replaced by Month 1 to 12

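### SAP 23.2.1.5 counts the 84-day exclusion after treatment withdrawal from two different dates, so the daily-entry sentence coded literally can keep data in DPS3 that section 13.5.3 excludes

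*SAP*

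**What the plan says.** The rule is stated in several places in the SAP.

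- Section 13.5.3 (long-term efficacy estimand) gives it twice. The intercurrent-event text says "data that occur beyond 12 weeks after their last infusion will not be considered". The estimator text describes the hypothetical strategy as working "by not including data collected 3 months or more after the latest infusion". The same section makes withdrawal from treatment an intercurrent event only when the primary reason is lack of efficacy or adverse events.
- Section 23.2.1.5 (data handling) opens consistently with this: "data that are collected 3 months or more after the latest infusion will be excluded". The next sentence is offered as the consequence for daily entries: "for the daily entries, data occurring 84 days or more after the date for withdrawal from treatment will be removed". For weekly entries it says "if at least one day of the 7-day period is covered by 84 days or more then data will be removed", without saying what the 84 days are counted from.
- Section 3.4 fixes the unit: "A Month is referring to a 28-day period".
- Chapter 6 defines DPS3 as leaving out, among others, "those following the 12-week rule after withdrawal from treatment", and refers to 23.2.1.5 for the detail.
- Chapter 2 explains how later data can exist: "Participants who are withdrawn from the treatment will be given the opportunity to remain in the trial at the discretion of the investigator". Those who stay are expected to follow all procedures except the infusion.

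**The concern.** A programmer building DPS3 is sent by chapter 6 to section 23.2.1.5, where the most specific instruction for daily entries uses a different start date from the estimand. The chapter 6 label, which mentions withdrawal and not infusion, leans the same way. Two programmers could build different DPS3 datasets from this text.

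The data at issue are those the hypothetical strategy is meant to leave out: attacks recorded more than 12 weeks after the last infusion in someone no longer treated. DPS3 feeds the long-term estimand, the continuous eDiary endpoints in 13.5.6.1 and responder status in 13.5.6.2. The all-data sensitivity analysis in 13.5.9.2 covers only the 13.5.3 endpoint. The LOCF and worst-case analyses in 13.5.9.3 cover only 75% response and themselves use DPS3. Neither settles the start date. The short-term estimands use DPS2 and are not touched.

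**Working it through.** **Length of the interval.** 3 months × 28 days (section 3.4) = 84 days, and 12 weeks × 7 days = 84 days. The plan's figure is reproduced; only the start date differs.

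**Are the two dates the same?** No. Section 13.5.5 lists time to withdrawal from treatment and time since the last infusion as separate items. Section 23.2.14 sets the treatment-withdrawal time to the study-withdrawal time when only the latter was recorded. Nothing equates the withdrawal date with the last infusion date.

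**Both sentences applied together.** Let w be the days from latest infusion to withdrawal, w ≥ 0. Sentence one removes data from day 84 after the infusion, and sentence two from day w + 84. Since 84 ≤ w + 84, sentence one always removes at least as much, so nothing extra stays.

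**Daily-entry sentence coded alone.** Inputs: daily entry in Weeks 1–4, 13–16, 25–28 and 37–40, and weekly entry otherwise (chapter 2); infusions on nominal Days 0, 84, 168 and 252; planned diary days 0–335; complete diary. For a latest infusion on Day 0, 84 or 168, the next daily block would cover days 84–111 after it, if daily entry resumes by calendar week without an infusion. Extra daily entries kept = min(w, 28). The last column also counts weekly entries from the withdrawal date.

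| w (days) | First excluded day, from latest infusion | First excluded day, from withdrawal | Extra daily entries | Extra weekly entries |
|---|---|---|---|---|
| 0 | 84 | 84 | 0 | 0 |
| 14 | 84 | 98 | 14 | 0 |
| 28 | 84 | 112 | 28 | 0 |
| 42 | 84 | 126 | 28 | 2 |
| 56 | 84 | 140 | 28 | 4 |
| 84 | 84 | 168 | 28 | 8 |

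The last row is a withdrawal dated at the next planned infusion visit: 28 + 8 × 7 = 84 days, and 84 / 28 = 3 monthly scores.

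**Lower end.** If daily entry needs an actual infusion, no daily entries exist from day 84. With weekly entries cut at the latest infusion, nothing extra stays.

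**After the fourth infusion.** 252 + 84 = 336, and the planned diary ends on day 335, so the effect is zero.

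**From entries to scores.** Turning retained entries into weekly or monthly scores needs a week number after a missed infusion. Section 23.2.1.4 and Panel 6 count weeks from each infusion and run Week 12 until the next one, so they give no Week 13 when that infusion does not happen. Only on the added assumption of calendar weeks from the first infusion can effects on responder eligibility (23.2.1.7) be worked out:

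- Daily entries only, w ≥ 11: two further weeks have at least 4 observed days (7 + 4 = 11), which makes one further month. Months 1–6 (last infusion Day 0) or Months 7–12 (last infusion Day 168) go from 3 to 4 of 6 observed months, reaching the threshold of 4.
- Weekly entries also from withdrawal, w = 84: the next 3-month period goes from 0 to 3 of 3 months (threshold 2). With the last infusion on Day 84, Months 1–12 goes from 6 to 9 of 12 (threshold 8).

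**The case against.** The intended rule is clear. Every statement of the principle (twice in 13.5.3, once in 23.2.1.5) starts from the last infusion, and the disputed sentence presents itself as following from the one before it. Harm requires someone to code a dependent sentence alone. This stands in part: the intent can be recovered, and the paragraph taken as a whole keeps nothing extra. But the sentence is an operational instruction and does not follow from its premise, and the weekly sentence does not settle the matter.

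The group is narrow. It needs withdrawal for lack of efficacy or adverse events, before the fourth infusion, in someone who stays and keeps the diary. Those who leave the study at the same time have no later diary data. This stands.

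The consequence is limited. The primary endpoints are safety endpoints, section 13.2 rules out formal testing, and the all-data analysis in 13.5.9.2 retains everything the disputed sentence could keep. This stands for the long-term attack endpoint. It does not cover the other DPS3 endpoints or show which DPS3 was built.

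A reader might go further and infer that each affected participant gains a fixed number of weekly scores, or that responder eligibility changes only for certain six-month periods. The documents do not support either. Both need a week assignment that Panel 6 does not give, and the second also needs the weekly entries to be cut at the latest infusion, which the text leaves open.

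**Conclusion.** Section 23.2.1.5 contradicts itself on the start date, and its daily-entry sentence conflicts with section 13.5.3. This is a derivation rule that is wrong as written. A reader might infer that the long-term estimand itself is undefined; it is not, because 13.5.3 is consistent and supplies the answer.

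The effect on the estimates cannot be computed: the documents give neither the number of participants concerned nor their withdrawal dates. Per participant it is:

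- zero if both sentences are applied, or after the fourth infusion;
- zero if daily entry needs an infusion and weekly entries are cut at the latest infusion;
- up to 28 daily entries if daily entry resumes by calendar week;
- as much as 84 days, or 3 monthly scores, if the weekly sentence is also read from the withdrawal date and withdrawal is dated at the next planned infusion visit.

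These figures assume nominal visit days and a complete diary. Any statement in monthly scores or responder eligibility also assumes calendar weeks after a missed infusion. The number affected is probably small. I rate this as a minor wording correction to a derivation rule.

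**What to change.** Replace the daily- and weekly-entry sentences on withdrawal in SAP 23.2.1.5 with, for example:

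> For participants withdrawn from treatment (as defined in section 13.5.3), each daily entry dated 84 days or more after the latest infusion is removed; each weekly entry is removed when any day of its 7-day period falls 84 days or more after the latest infusion.

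The opening condition matters. Without it, a continuing participant infused a few days late within the ±3-day visit window could lose a Week 12 entry. Optionally, reword the DPS3 label in chapter 6 so that it also names the latest infusion.

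The cost is a line or two of SAP text and one date variable in the DPS3 derivation, with no change to data collection. The only downside is slightly fewer data points in DPS3 than under the literal daily-entry reading.
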